## LIST OF ABBREVIATIONS

AE	adverse event
ALT	alanine aminotransferase
anti-HBc	anti-hepatitis B core antibodies
AST	aspartate aminotransferase
ATP	adenosine triphosphate
ATPase	adenosine triphosphatase
β-hCG	β-human chorionic gonadotropin
BCG	Bacillus Calmette–Guérin
BMI	body mass index
Bpm	beats per minute
BSA	body surface area
BUN	blood urea nitrogen
CK	creatine kinase
CRF	case report form
CYP450	cytochrome P450
DLQI	Dermatology Life Quality Index
ECG	electrocardiogram
ET	early termination (visit)
FDA	Food and Drug Administration
FSH	follicle-stimulating hormone
GCP	Good Clinical Practice
GGT	gamma-glutamyltransferase
HBsAg	hepatitis B surface antigens
HBV	hepatitis B virus
HCT	hematocrit
HCV	hepatitis C virus
Hgb	hemoglobin
HIV	human immunodeficiency virus
IB	Investigator's Brochure
ICH	International Council for Harmonisation
IL	interleukin
IRB	institutional review board
ITT	intent-to-treat (population)
LDH	lactate dehydrogenase
LMW	low molecular weight
MCH	mean corpuscular hemoglobin
MCHC	mean corpuscular hemoglobin concentration
MCV	mean corpuscular volume
MPV	mean platelet volume
MTD	maximum tolerated dose
NRS	Numeric Rating Scale
NSAID	nonsteroidal anti-inflammatory drug
PASI	Psoriasis Area and Severity Index

PBMC	peripheral blood mononuclear cell
PGA	Physician's Global Assessment
PK	pharmacokinetics
PP	per-protocol (population)
PPD	purified protein derivative
RBC	red blood cell (count)
REB	research ethics board
RT-PCR	reverse transcription polymerase chain reaction
SAE	serious adverse event
SAF	safety (population)
TB	tuberculosis
TEAE	treatment-emergent adverse events
TNF	tumor necrosis factor
ULN	Upper Limit of Normal
WBC	white blood cell (count)

## SUMMARY

**Title:** A Phase 1b, open-label, singlecenter, single-arm, dose-selection, proof-of-concept study to assess the safety and efficacy of a novel HSP90 inhibitor (CUDC-305) in the treatment of moderate to severe plaque psoriasis

**Phase:** 1b

**Population:** Approximately 12 and not exceeding 16 male or female subjects aged 18 years or older with moderate to severe plaque psoriasis will be included in this study.

**Number of Sites:** One center in Denmark will participate in this study.

**Study Duration:** Subject participation will be approximately 20 weeks, involving a 4-week screening phase, a 12-week treatment phase, and a 4-week observational follow-up phase to assess for psoriasis relapse and flare.

### Objectives:

#### Primary:

- To determine the optimal efficacious dose-range of CUDC-305 in the treatment of moderate to severe plaque psoriasis in a Phase 1b proof-of-concept study

#### Secondary:

- To evaluate the safety and tolerability of CUDC-305 in the treatment of moderate to severe plaque psoriasis
- To investigate changes in skin and blood biomarkers

### Endpoints:

#### Primary Efficacy Endpoint:

- Change from baseline in Psoriasis Area and Severity Index (PASI) score at Week 12

#### Secondary Efficacy Endpoints:

- Proportion of subjects with Physician's Global Assessment (PGA) of clear or almost clear at Weeks 2, 4, 8, 12, and 16
- Change and percent change from baseline in body surface area (BSA) covered with plaque psoriasis at Weeks 2, 4, 8, 12, and 16
- Change and percent change from baseline in BSA multiplied by the PGA at Weeks 2, 4, 8, 12, and 16

- Proportion of subjects achieving 50%, 75%, and 90% reduction from baseline in PASI at Weeks 2, 4, 8, 12, and 16
- Change and percent change from baseline in PASI scores at Weeks 2, 4, 8, and 16
- Percent change from baseline in PASI scores at Week 12
- Change from baseline in pruritus Numeric Rating Scale (NRS) at Weeks 2, 4, 8, 12, and 16
- Change from baseline in the Dermatology Life Quality Index (DLQI) total score at Weeks 4, 8, 12, and 16
- Change from baseline in skin and blood biomarkers at Weeks 4, 8, and 12

**Secondary Safety Endpoints:**

- Incidence of treatment-emergent adverse events (TEAEs)
- Incidence of related TEAEs

**Overall Study Design:**

This is a 12-week treatment, singlecenter, open-label, single-arm, dose-selection, proof-of-concept study to determine a dosage of CUDC-305 that is tolerable and demonstrates preliminary efficacy for use in future efficacy Phase 2 trials.

Eligible subjects will be sequentially assigned to one of the four cohorts (approximately n = 4 per cohort) receiving ascending or descending doses of CUDC-305. The first cohort will be administered a starting oral dose of 250 mg/d for 12 weeks, which is believed to be the target effective dose for treatment of psoriasis. The dose regimen to be administered to the subsequent cohort will be decided after reviewing the safety and efficacy data of the first four subjects completing the treatment period (12 weeks) in the current cohort. A safety meeting will take place to review the available data prior to deciding the next dose and then initiating dosing of the subsequent cohort. The doses that will be evaluated in this study range between 100 mg and 1000 mg and may include: 100 mg, 250 mg, 500 mg, 800 mg, or 1000 mg orally once daily.

The sponsor and principal investigator(s) will jointly evaluate the safety and tolerability of CUDC-305 at the safety meeting, and intolerance will be determined by taking into account all information from adverse events (AEs), vital signs, physical examination findings, laboratory abnormalities, and electrocardiogram (ECG) findings. The study may be stopped permanently or interrupted at any time for safety reasons.

PASI, PGA, BSA, pruritus NRS, and DLQI will be performed to assess efficacy. Safety will be assessed with the vital signs, physical examination, clinical laboratory tests, ECG, and collection of AEs.

Skin biopsies will be collected from nonlesional and lesional skin for immunohistochemistry and gene expression analysis.

Medical photographs of the target lesion will also be performed at each study visit (except the screening visit).

## **Inclusion Criteria:**

Subjects will be eligible to be enrolled in the study if they meet all of the following criteria at the screening and baseline (Day 0) visits, unless specified otherwise:

1. Men or women aged 18 years or older at the time of consent.
2. Subject has a history of plaque psoriasis for at least 6 months prior to the screening visit.
3. Subject has stable psoriasis conditions for at least 3 months before screening, according to subject.
4. Subject has plaque psoriasis covering  $\geq 3\%$  of his total BSA at baseline (Day 0).
5. Subject has a PASI score of  $\geq 6$  at baseline (Day 0).
6. Subject has a PGA score of  $\geq 3$  at baseline (Day 0).
7. Subject has a body mass index (BMI)  $\leq 40 \text{ kg/m}^2$ .
8. Subject is a candidate for phototherapy or systemic treatment of psoriasis (either naïve or has a history of previous treatment).
9. Subjects (women and men) involved in any sexual intercourse that could lead to pregnancy must agree to use an effective contraceptive method from at least 4 weeks before baseline (Day 0) until at least 4 weeks after the last study product administration for the duration of the study. Effective contraceptive methods are: systemic hormonal contraceptives (oral contraceptive, patch, vaginal ring, injectables, or implants), intrauterine devices, vasectomy, or barrier methods of contraception in conjunction with spermicide. Hormonal contraceptives must be on a stable dose for at least 4 weeks before baseline (Day 0).

Note: Women of nonchildbearing potential are as follows:

- Women who have had surgical sterilization (hysterectomy, bilateral oophorectomy, bilateral salpingectomy, or bilateral tubal ligation)
- Women  $\geq 60$  years of age
- Women  $>40$  and  $<60$  years of age who have had a cessation of menses for at least 12 months and a follicle-stimulating hormone (FSH) test confirming nonchildbearing potential (FSH  $\geq 40 \text{ mIU/mL}$ ) or cessation of menses for at least 24 months without FSH levels confirmed

10. Women of childbearing potential must have a negative serum pregnancy test at screening and negative urine pregnancy test at baseline (Day 0).
11. Subject must have negative tuberculosis (TB) infection tests. Subject will be evaluated for latent TB infection with a purified protein derivative (PPD) test, T-spot test or a Quantiferon Gold test, and with a chest x-ray, if one has not been performed in the last 6 months. Subject who demonstrates evidence of latent TB infection (either PPD greater than or equal to 5 mm of induration or positive Quantiferon Gold or T-spot test, irrespective of *Bacillus Calmette–Guérin* (BCG) vaccination status and negative chest x-ray findings for active TB, or suspicious chest x-ray findings) will not be allowed to participate in the study.

12. Subject must be willing to participate and must be capable of giving informed consent, and the consent must be obtained prior to any study-related procedures.

#### **Exclusion Criteria:**

Subjects will not be eligible for participation in the study if they meet any of the following criteria at the screening and baseline (Day 0) visits, unless specified otherwise:

1. Female subject who is breastfeeding, pregnant, or who is planning a pregnancy during the study.
2. Subject has evidence of erythrodermic, pustular, predominantly guttate psoriasis, or drug-induced psoriasis.
3. Subject has a history of skin disease or presence of skin condition that, in the opinion of the investigator, would interfere with the study assessments.
4. Subject is known to have immune deficiency or is immunocompromised.
5. Subject has a history of cancer or lymphoproliferative disease within 5 years prior to baseline (Day 0). Subjects with successfully treated non-metastatic cutaneous squamous cell or basal cell carcinoma and/or localized carcinoma in situ of the cervix are not to be excluded.
6. Subject has had a major surgery within 8 weeks prior to baseline (Day 0) or has a surgery planned during the study.
7. Subject has any clinically significant medical condition or physical/laboratory/ECG/vital signs abnormality that would, in the opinion of the investigator, put the subject at undue risk or interfere with interpretation of study results.
8. Subject has alanine aminotransferase (ALT) or aspartate aminotransferase (AST) values  $\geq 2$  times the upper limit of normal (ULN) at screening.
9. Subject has absolute neutrophil count  $\leq 1,5 \times 10^9/L$  or platelet count  $\leq 100 \times 10^9/L$  at screening.
10. Subject has history of clinically significant anemia or hemoglobin (Hgb) value  $\leq 10 \text{ g/dL}$  at screening.
11. Subject has a creatinine clearance  $\leq 60 \text{ ml/min}$  at screening (calculated with Cockcroft-Gault formula)
12. Subject with positive results for hepatitis B surface antigens (HBsAg), anti-hepatitis B core antibodies (anti-HBc), hepatitis C virus (HCV), or human immunodeficiency virus (HIV).
13. Subject has a known or suspected allergy to CUDC-305 or any component of the investigational product.
14. Subject has a history of clinically significant drug or alcohol abuse in the last year prior to baseline visit (Day 0).

15. Subject is currently receiving an investigational product or device or has received one within 4 weeks prior to baseline visit (Day 0).
16. Subject has used biologics medication 12 weeks prior to baseline visit (Day 0), or 5 half-lives (whichever is longer).
17. Subject has used any systemic treatment for psoriasis (including corticosteroids, oral retinoids, immunosuppressive medication, methotrexate, cyclosporine, or apremilast) within 4 weeks prior to baseline visit (Day 0).
18. Subject has used any topical medication to treat psoriasis (including corticosteroids; retinoids; vitamin D analogues, such as calcipotriol; or tar) within 2 weeks prior to baseline visit (Day 0).
19. Subject had any UVB phototherapy (including tanning beds) or excimer laser within 2 weeks prior to baseline visit (Day 0).
20. Subject had PUVA treatment within 4 weeks prior to baseline visit (Day 0).
21. Subject has received a live attenuated vaccine within 4 weeks prior to baseline visit (Day 0) or plan to receive a live attenuated vaccine during the study and up to 1 month after the last study drug administration. Subject had excessive sun exposure within 2 weeks prior to baseline visit (Day 0), or is planning a trip to a sunny climate, or is not willing to minimize natural and artificial sunlight exposure during the study. Use of sunscreen products and protective apparel are recommended for other circumstances when exposure cannot be avoided. Sunscreen must not be applied on the clinic visit days before the visit.
22. Subject has a history of an allergic reaction or significant sensitivity to lidocaine or other local anesthetics.
23. Subject has a history of hypertrophic scarring or keloid formation in scars or suture sites.
24. Subject is taking anticoagulant medication, such as heparin, low molecular weight (LMW)-heparin, warfarin, antiplatelets (nonsteroidal anti-inflammatory drugs [NSAIDs] and low-dose aspirin that is equal or lower than 81 mg will not be considered antiplatelets), or has a contraindication to skin biopsies.

### **Statistical Analysis:**

Because of the nature and design of the study, the statistical analysis will be mainly descriptive.

Descriptive summaries of demographics, baseline characteristics, and subject disposition will be presented by dose regimen and overall. Continuous variables will be summarized by dose regimen and overall in tables and will include the number of subjects, mean, standard deviation, median, minimum, maximum, and range. Categorical variables will be presented by dose regimen and overall in tables as frequencies and percentages.

No formal sample size calculations were conducted. Four subjects will be enrolled into each cohort, for a total of a maximum of 16 subjects. This sample size was selected to allow sufficient characterization of the drug's safety profile over the planned doses range and to allow for

preliminary efficacy assessment of CUDC-305 in subjects with moderate to severe plaque psoriasis.

## 1 BACKGROUND

Psoriasis is a chronic inflammatory skin disease characterized by immune dysregulation of unknown etiology affecting over 25 million individuals worldwide (1, 2). Psoriasis can become debilitating and severely impact quality of life, well-being and personal interactions (3, 4). An estimated 25% of patients suffer moderate to severe disease forms that require systemic therapy with immune suppressants and ultraviolet phototherapy (5, 6). Despite advances in the development of targeted biologics including TNF, IL-12/23 and IL-17 inhibitors, most psoriasis patients remain inadequately treated and dissatisfied with the therapy they are receiving (7, 8). Due to the risk of serious adverse side effects associated with these therapies, patients are often required to alternate between various therapeutic modalities as a precautionary measure. There is a pressing need for the clinical development of effective, safe, easy to use, and affordable psoriasis therapeutics that target the upstream proteomic mediators of the disease.

Human psoriatic lesions display a profound upregulation of HSP90 as compared to normal skin which is thought to be partially associated with IL-17 production (9, 10). CUDC-305 (previously called Debio 0932) is a novel small molecule HSP90 inhibitor which displays promising pharmacological properties for drug development in psoriasis such as good oral bioavailability, potent HSP90 inhibition, accumulation in the skin (as demonstrated in preclinical models), no ocular toxicity, a good safety profile (demonstrated in a Phase 1 oncology dose escalation study), a pharmacokinetic profile (high first-pass metabolism) that permits rapid flexibility in terms of dose-control/ therapy discontinuation, and targeting of multiple upstream mediators of inflammatory pathways. Clinical investigation in psoriasis is supported by evaluation of anti-psoriatic potential in human epidermal keratinocyte and monocytic cell lines showing that HSP90 inhibition with CUDC-305 is highly effective in inhibiting proliferation in keratinocytes and monocytes, and reducing the secretion of inflammatory cytokines in activated monocytes and T-cells.

*second-line therapy of patients with Stage IIIb or IV Non-small Cell Lung Cancer - the HALO study (HSP90 inhibition And Lung cancer Outcomes)*, during Part A. It is important to highlight that this study was completed in patients with advanced cancers, specifically Stage IIIb and IV Non-small Cell Lung Cancer (NSCLC), where CUDC-305 administration was being evaluated in combination with cisplatin/pemetrexed and cisplatin/gemcitabine (naive Stage IIIb and IV NSCLC patients) or with docetaxel (previously treated Stage IIIb and IV NSCLC). The proposed trial is designed as a dose-ranging trial in order to explore dose and define the maximum tolerated dose and viable Phase 2 doses in patients with moderate to severe psoriasis (the target population); a unique population that is quite disparate from that of previous trials. Furthermore, discontinuation of the referenced Phase 2 studies were not based on safety concerns and that all safety observations from these studies “were consistent with the previously observed side effects.” Finally, preclinical studies found that CUDC-305 accumulated in dermal tissues versus plasma(11). In a xenograft mouse model of psoriasis daily dosing of CUDC-305 lead to plasma levels of ~2uM and skin levels of ~24 pmol/mg of wet tissue 30 minutes post-dosing on the final treatment day, representing a concentration in skin that exceeds the IC50 (~0.1  $\mu$ M) of CUDC-305 for HSP90 $\alpha/\beta$  (based on the assumption that 1mg of tissue equals 1 ml of biological fluid and taking in to account the 6% unbound plasma fraction of CUDC-305). This suggests that concerns with reduced efficacy being associated with poor oral bioavailability may be less relevant in dermal indications, such as psoriasis.

## **2 STUDY OBJECTIVES**

### **2.1 Primary Objective**

The primary objective is as follows:

- To determine the optimal efficacious dose-range of CUDC-305 in the treatment of moderate to severe plaque psoriasis in a Phase 1b proof-of-concept study

### **2.2 Secondary Objectives**

The secondary objectives are as follows:

- To evaluate the safety and tolerability of CUDC-305 in the treatment of moderate to severe plaque psoriasis
- To investigate changes in skin and blood biomarkers

## 3 STUDY ENDPOINTS

### 3.1 Primary Endpoint

The primary efficacy endpoint is as follows:

- Change from baseline in Psoriasis Area and Severity Index (PASI) score at Week 12

### 3.2 Secondary Endpoints

The secondary endpoints are as follows:

#### Efficacy Endpoints

- Proportion of subjects with Physician's Global Assessment (PGA) of clear or almost clear at Weeks 2, 4, 8, 12, and 16
- Change and percent change from baseline in body surface area (BSA) covered with plaque psoriasis at Weeks 2, 4, 8, 12, and 16
- Change and percent change from baseline in BSA multiplied by the PGA at Weeks 2, 4, 8, 12, and 16
- Proportion of subjects achieving 50%, 75%, and 90% reduction from baseline in PASI at Weeks 2, 4, 8, 12, and 16
- Change and percent change from baseline in PASI scores at Weeks 2, 4, 8, and 16
- Percent change from baseline in PASI scores at Week 12
- Change from baseline in pruritus Numeric Rating Scale (NRS) at Weeks 2, 4, 8, 12, and 16
- Change from baseline in the Dermatology Life Quality Index (DLQI) total score at Weeks 4, 8, 12, and 16
- Change from baseline in skin and blood biomarkers at Weeks 4, 8, and 12

#### Safety Endpoints

- Incidence of treatment-emergent adverse events (TEAEs)
- Incidence of related TEAEs

## 4 STUDY DESIGN

This is a 12-week treatment, singlecenter, open-label, single-arm, dose-selection, proof-of-concept study to determine a dosage of CUDC-305 that is tolerable and demonstrates preliminary efficacy for use in future efficacy Phase 2 trials.

Eligible subjects will be sequentially assigned to one of the four cohorts (approximately n = 4 per cohort) receiving ascending or descending doses of CUDC-305. The first cohort will be administered a starting oral dose of 250 mg/d for 12 weeks, which is believed to be the target effective dose for treatment of psoriasis. The dose regimen to be administered to the subsequent cohort will be decided after reviewing the safety and efficacy data of the first four subjects completing the treatment period (12 weeks) in the current cohort. A safety meeting will take place to review the available data prior to deciding the next dose and then initiating dosing of the subsequent cohort. The doses that will be evaluated in this study range between 100 mg and 1000 mg and may include: 100 mg, 250 mg, 500 mg, 800 mg, or 1000 mg orally once daily.

The sponsor and principal investigator(s) will jointly evaluate the safety and tolerability of CUDC-305 at the safety meeting, and intolerance will be determined by taking into account all information from adverse events (AEs), vital signs, physical examination findings, laboratory abnormalities, and electrocardiogram (ECG) findings. The study may be stopped permanently or interrupted at any time for safety reasons.

PASI, PGA, BSA, pruritus NRS, and DLQI will be performed to assess efficacy. Safety will be assessed with the vital signs, physical examination, clinical laboratory tests, ECG, and collection of AEs.

Skin biopsies will be collected from nonlesional and lesional skin for immunohistochemistry and gene expression analysis.

Medical photographs of the target lesion will also be performed at each study visit (except the screening visit).

A schedule of events is presented in Section 7.

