## 5 STUDY POPULATION

This study will include approximately 16 subjects with moderate to severe plaque psoriasis. Subjects will be men or women, aged 18 years or older.

Subjects who are discontinued after taking the first dose of study product will not be replaced.

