### **5.3 Discontinuations**

Subjects have the right to withdraw from the study at any time for any reason without penalty. The investigator also has the right to withdraw subjects from the study if he or she feels it is in the best interest of the subject or if the subject is uncooperative or noncompliant.

Should a subject decide to withdraw, all efforts will be made to complete and report the observations as thoroughly as possible, particularly the follow-up examination.

The investigator or one of his or her staff members should contact the subject to determine as completely as possible the reason for the withdrawal. A complete final evaluation at the time of the subject's withdrawal should be made with an explanation of why the subject is withdrawing from the study. If the reason for removal of a subject is an AE or an abnormal laboratory test result, the principal specific event or test will be recorded. The criteria for enrollment must be followed explicitly. Subjects who discontinue the study after taking his or her first dose will be asked, if they agree, to come for a last assessment (early termination visit). Subjects who discontinue will not be replaced.

Reasons for discontinuation include the following:

- The investigator decides that the subject should be withdrawn. If this decision is made because of a serious adverse event (SAE), the study product is to be discontinued immediately and appropriate measures are to be taken. The investigator will notify the sponsor immediately.
- The attending physician requests that the subject be withdrawn from the study.
- The subject, for any reason, requires treatment with another therapeutic agent that has been demonstrated to be effective for treatment of the study indication. In this case, discontinuation from the study occurs immediately upon introduction of the new agent.
- The subject is lost to follow-up. In this case, a reasonable attempt to contact the subject and ascertain his or her status must be made, and these attempts must be documented.
- The sponsor or regulatory authorities, for any reason, stop the study. In this case, all subjects will be discontinued from the study and notified of the reasons for the discontinuation.
- The subject has become pregnant at any time during the study.
- Other: the subject may withdraw from the study for any other reason, including withdrawal of consent.

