#### 6.2.6 Method of Assignment to Treatment Dose

Eligible subjects will be sequentially assigned to one of the four cohorts (approximately n = 4 per cohort) receiving ascending or descending doses of CUDC-305. The first cohort will be administered a starting oral dose of 250 mg/d which is believed to be the target effective dose for treatment of psoriasis. The dose regimen to be administered to the subsequent cohort will be decided after reviewing the safety and efficacy data of the first four subjects completing the treatment period (12 weeks) in the previous cohort. The dose regimen of the subsequent cohort could be higher or lower, according the safety and efficacy data of the previous cohort. A safety meeting will take place to review the available data prior to deciding the next dose and then initiating dosing of the subsequent cohort. The study may be stopped permanently or interrupted at any time for safety reasons following review of study data.

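### Section 10.1's six per cohort contradicts the four per cohort and the cap of 16, and a next-dose decision tied to four completers cannot be met as worded after one dropout in a cohort of four

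*Protocol*

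**What the plan says.** **Cohort size.** The Summary, under Statistical Analysis, states: "Four subjects will be enrolled into each cohort, for a total of a maximum of 16 subjects". Section 10.1 carries nearly the same sentence with six in place of four and the same maximum of 16. Section 4, the Summary's design paragraph and Section 6.2.6 describe four sequential cohorts of approximately four. Section 5 says: "This study will include approximately 16 subjects with moderate to severe plaque psoriasis". The Summary's population entry gives about 12 and no more than 16.

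**Next-dose decision.** Section 4 and the Summary decide the next cohort's dose after "reviewing the safety and efficacy data of the first four subjects completing the treatment period (12 weeks) in the current cohort". Section 6.2.6 says the same from the next cohort's viewpoint: "reviewing the safety and efficacy data of the first four subjects completing the treatment period (12 weeks) in the previous cohort". Section 4 then adds: "A safety meeting will take place to review the available data prior to deciding the next dose".

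**Replacement.** Section 5: "Subjects who are discontinued after taking the first dose of study product will not be replaced". Section 5.3: "Subjects who discontinue will not be replaced".

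**Power statement.** Section 10.2 claims 80% power at 95% confidence for a Wilcoxon signed-rank test of the Week 12 PASI change if the effect is at least 1.23 SD. It gives no sample size, no sidedness, and no indication whether the test is per cohort or pooled.

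**The concern.** Section 10.1 is where a reader looks for the sample size, and its cohort size disagrees with the rest of the protocol and with its own total. The intended size of each dose group is therefore unclear, and the 1.23 SD figure cannot be tied to any size that the design names.

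The rule for moving to the next dose needs four completers. If a cohort is four subjects and nobody is replaced, the rule has no tolerance for a single discontinuation, including one for toxicity. Finding the dose range is the primary objective and this step is how doses are chosen, so the protocol should say what happens when fewer than four complete. It does not.

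**Working it through.** **1. Cohort size against the cap.** Inputs: four cohorts (Section 4), maximum 16 (Summary and Section 10.1), four per cohort (Summary), six per cohort (Section 10.1).

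- Four per cohort: 4 × 4 = 16. This reproduces the stated maximum.
- Six per cohort: 4 × 6 = 24, which is 8 over the maximum. Three cohorts of six (3 × 6 = 18) also exceed it. Since 16/6 = 2.67, only two full cohorts of six fit.

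**2. The 1.23 SD figure.** Check: power of the exact signed-rank test at the 5% level for normally distributed changes with mean 1.23 SD, from 100,000 simulated samples per n.

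| n | One-sided power | Two-sided power |
|---|---|---|
| 4 | 0 | 0 |
| 6 | 0.797 | 0.502 |
| 8 | 0.892 | 0.786 |
| 12 | 0.986 | 0.959 |
| 16 | 0.998 | 0.993 |

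The stated 80% is matched at n = 6 one-sided and nearly matched at n = 8 two-sided. For n = 6 one-sided, a noncentral-t approximation with Wilcoxon efficiency 3/π gives a required effect of 1.226 SD. The figure fits neither a cohort of four nor a pooled 12 or 16. At n = 4 there are 2⁴ = 16 sign patterns, so the smallest exact p is 1/16 = 0.0625 one-sided and 2/16 = 0.125 two-sided. Neither is below 0.05, so the test cannot reject whatever the effect.

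**3. The four-completer condition.** With four dosed and no replacement, one dropout leaves at most 4 − 1 = 3 completers. The protocol gives no dropout rate, so p below is an assumption, with subjects independent and equal p. The table shows the chance that a cohort yields fewer than four completers.

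| p | Four dosed: 1 − (1−p)⁴ | Five dosed: 1 − [(1−p)⁵ + 5p(1−p)⁴] |
|---|---|---|
| 5% | 1 − 0.8145 = 0.1855 | 1 − 0.9774 = 0.0226 |
| 10% | 1 − 0.6561 = 0.3439 | 1 − 0.9185 = 0.0815 |
| 20% | 1 − 0.4096 = 0.5904 | 1 − 0.7373 = 0.2627 |

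Four cohorts involve three next-dose decisions. With four per cohort, all three have their four completers with probability (1−p)¹²: 0.540, 0.282 and 0.069 at 5%, 10% and 20%.

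**4. Is there slack under the cap?** Reading approximately four as five: three cohorts need 3 × 5 = 15, which fits, and both decisions are met with probability 0.9185² = 0.844 at 10% dropout or 0.7373² = 0.544 at 20%. Four cohorts need 4 × 5 = 20, which does not fit. Four full cohorts of four use all 16 places.

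**The case against.** The strongest reply is that the decision rule is looser than its wording. Section 10.2.4 provides for ongoing reviews of available safety and preliminary efficacy data to guide the dose decisions. Section 15.4 requires all available data to be reviewed before a later cohort is dosed, with agreement of all parties in a signed decision. Section 4 judges intolerance on all adverse-event, laboratory and ECG information, not on completers alone, and the study can be stopped at any time. Section 5.3 asks for a final evaluation at withdrawal. Cohort size is only approximate, the phrase about the first four to complete suggests a cohort could be larger, and a three-cohort trial has spare places. The dropout rates are assumed, and the analysis is mainly descriptive.

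Most of this stands, and it limits the consequence. A reader might infer that losing a subject to toxicity lets the team escalate blind to that event; the documents do not support that, because the subject's data are reviewed in any case. What remains is that no sentence reconciles four completers with available data or says when the decision is due if only three complete. Nor does the approximate cohort size help if all four planned cohorts run.

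On the power figure, it is fair to say that Section 10.2 does not make the test per cohort. The zero-power result at four therefore applies only on that reading. A reader might also infer that 1.23 SD proves a leftover six-per-cohort design; the near match at eight two-sided, though the protocol names no such n, leaves that as inference.

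**Conclusion.** The cohort-size contradiction is certain and needs no assumption: six per cohort conflicts with four elsewhere and cannot give four cohorts within 16. The 1.23 SD figure cannot be interpreted without its n and sidedness, and it matches no sample size that the current design supports.

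The four-completer condition fails as worded after one post-dose dropout in a cohort of four. The 19%, 34% and 59% are illustrations at assumed dropout of 5%, 10% and 20%. They measure how often the literal condition fails, not any effect on the dose chosen or on safety. The practical result is delay, or a decision made without a stated rule.

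A reader might also set Section 15.4's bar on higher doses against the discretionary wording of Section 6.2.7. The two are compatible, since following Section 15.4 satisfies both, so that is not part of this point.

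This should be fixed, but it is a correction of wording and not a flaw that endangers subjects.

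**What to change.** - **Section 10.1:** change six to four, to agree with the Summary and the maximum of 16.
- **Section 10.2, in the same edit:** state the n, the sidedness and whether the test is per cohort or pooled for the 1.23 SD figure, or remove the statement.
- **Summary (design paragraph), Section 4 and Section 6.2.6:** replace the four-completer condition with a rule that the next-dose decision is made once every dosed subject in the cohort has completed Week 12 or discontinued, using all data, including those from discontinued subjects.

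The cost is protocol amendment wording. No extra subjects, visits or procedures are needed.
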